## LIST OF ABBREVIATIONS

Abbreviations and Special Terms	Definition
AE	adverse event
AJCC	American Joint Committee on Cancer
ALT	alanine aminotransferase
ANC	absolute neutrophil count
aPTT	activated partial thromboplastin time
AST	aspartate aminotransferase
[REDACTED]	[REDACTED]
CFR	Code of Federal Regulations
CNS	central nervous system
COVID-19	coronavirus disease 2019
CR	complete response
CT	computed tomography
CTCAE	Common Terminology Criteria for Adverse Events
CYP	cytochrome P450
[REDACTED]	[REDACTED]
DDI	drug-drug interaction
DOR	duration of response
ECG	Electrocardiogram
ECOG	Eastern Cooperative Oncology Group
eCRF	electronic case report form
EDC	electronic data capture
EMA	European Medicines Agency
[REDACTED]	[REDACTED]
EOT	end of treatment
[REDACTED]	[REDACTED]
FDA	Food and Drug Administration
FGFR	fibroblast growth factor receptor
FGFR1-3	fibroblast growth factor receptors 1, 2, or 3
GCP	Good Clinical Practice
HBV	hepatitis B virus

Abbreviations and Special Terms	Definition
HCV	hepatitis C virus
HIPAA	Health Insurance Portability and Accountability Act of 1996
HP	hyperphosphatemia
IB	Investigator's Brochure
IC 50	concentration that results in 50% inhibition
ICF	informed consent form
ICH	International Council on Harmonization of Technical Requirements for Registration of Pharmaceuticals for Human Use
ICR	Independent Central Review
IEC	independent ethics committee
IMP	investigational medicinal product
INR	international normalized ratio
IRB	institutional review board
IRT	interactive response technology
MATE	multidrug and toxin extrusion
MedDRA	Medical Dictionary for Regulatory Activities
MRI	magnetic resonance imaging
NCI	National Cancer Institute
OAT	organic anion transporter
OATP	organic anion-transporting peptide
OCT	optical coherence tomography
OCT2	organic cation transporter 2
ORR	objective response rate
OS	overall survival
PBPK	physiologically based pharmacokinetic
[REDACTED]	[REDACTED]
PFS	progression-free survival
P-gp	p-glycoprotein
[REDACTED]	[REDACTED]
PMDA	Pharmaceuticals and Medical Devices Agency
PR	partial response
PT	prothrombin time

Abbreviations and Special Terms	Definition
PTH	parathyroid hormone
PTT	partial thromboplastin time
QD	once daily
[REDACTED]	[REDACTED]
RANO	Response Assessment in Neuro-Oncology
RECIST v1.1	Response Evaluation Criteria in Solid Tumors version 1.1
SAE	serious adverse event
SD	stable disease
SoA	schedule of activities
SOP	standard operating procedure
SRD/RPED	serous retinal detachment/retinal pigmented epithelium detachment
TEAE	treatment-emergent adverse event, AEs reported for the first time or worsening of a pre-existing event after first dose of study treatment
ULN	upper limit of normal

## 1. PROTOCOL SUMMARY

**Protocol Title:** A Phase 2, Open-Label, Single-Arm, Multicenter Study to Evaluate the Efficacy and Safety of Pemigatinib in Participants With Previously Treated Locally Advanced/Metastatic or Surgically Unresectable Solid Tumor Malignancies Harboring Activating FGFR Mutations or Translocations

**Protocol Number:** INCB 54828-207

### Objectives and Endpoints:

Table 1 presents the primary, secondary, [REDACTED] endpoints and objectives.

**Table 1: Primary and Secondary Objectives and Endpoints**

Objectives	Endpoints
Primary	
To evaluate the efficacy of pemigatinib in participants with locally advanced/metastatic or surgically unresectable solid tumor malignancy with an activating FGFR mutation or fusion/rearrangement.	ORR in Cohort A, defined as the proportion of participants in Cohort A who achieve a CR or PR based on RECIST v1.1 or RANO. ORR in Cohort B, defined as the proportion of participants in Cohort B who achieve a CR or PR based on RECIST v1.1 or RANO. An independent radiological review committee will determine response.
Secondary	

To evaluate other clinical efficacy measurements of pemigatinib in participants with locally advanced/metastatic or surgically unresectable solid tumor malignancy with an activating FGFR mutation and/or fusion/rearrangement.

Safety and tolerability of pemigatinib.

	

PFS, defined as the time from first dose until progressive disease (according to RECIST v1.1 or RANO and assessed by an ICR) or death (whichever is first) in Cohorts A and B, respectively.

DOR, defined as the time from the date of first assessment of CR or PR until the date of the first progressive disease by an ICR per RECIST v1.1 or RANO, or death (whichever is first) in Cohorts A and B, respectively.

OS, defined as the time from first dose of study drug to death of any cause in Cohorts A and B, respectively.

Safety and tolerability, as assessed by the occurrence of TEAEs and treatment-related AEs according to NCI CTCAE v5.0, physical exam changes, vital sign changes, laboratory evaluations, and ECGs in each cohort.

**Table 1: Primary and Secondary Objectives and Endpoints (Continued)**

Objectives	Endpoints

**Overall Design:**

[Table 2](#) presents the key study design elements. Further study details are presented after the table.

**Table 2: Key Study Design Elements**

Study Phase	Phase 2
Clinical Indication	Solid tumor malignancy
Population	Male and female participants at least 18 years of age who have a solid tumor malignancy with an activating FGFR mutation or fusion/rearrangement who have progressed on prior therapies and have no available standard treatment options
Number of Participants	Approximately 170 participants will be enrolled
Study Design	Single-arm, open-label, multicenter
Estimated Duration of Study Participation	Up to 35 days for screening, continuous treatment in consecutive 21-day cycles as long as participants are receiving benefit and have not met any criteria for study withdrawal, and 30 to 35 days for follow-up after the last dose of study drug. It is estimated that an individual will participate for approximately 6 months.
DSMB/DMC	Yes (internal)
Coordinating Principal Investigators	[REDACTED] [REDACTED], MD, PhD [REDACTED] Phone: [REDACTED] e-mail: [REDACTED] [REDACTED], MD [REDACTED] Phone: [REDACTED] e-mail: [REDACTED]

**Treatment Groups and Duration:**

This is an open-label, monotherapy study of pemigatinib in participants with advanced/metastatic or surgically unresectable solid tumor malignancy harboring an activating FGFR mutation or translocation, which will be referred to as fusion/rearrangement. The term "translocation" was initially used to describe the genomic alterations in this protocol. With increased understanding of FGFR1-3 genomic alterations in different tumor types, the terminology has evolved to rearrangements or fusions to more precisely describe these genomic alterations.

This study consists of 3 cohorts, Cohort A, Cohort B, and Cohort C, and will enroll approximately 60 participants, 90 participants, and 20 participants, respectively (see [Figure 1](#)). Participants will receive a QD dose of pemigatinib at 13.5 mg continuously as long as participants are receiving benefit and have not met any criteria for study withdrawal. Participants with local laboratory test results (eg, tissue or plasma-based molecular assays) documenting an activating FGFR1, FGFR2, or FGFR3 mutation or gene rearrangement are eligible to enroll as long as the results meet the cohort criteria. Confirmatory testing through the central genomics laboratory will be performed for all participants; however, results from the

central genomics laboratory are not required before enrollment. Centralized genomic testing results will allow participants to be assigned to a cohort (see [Appendix C](#) for list of alterations):

- Cohort A: FGFR1-3 in-frame fusions; any FGFR2 rearrangement; FGFR1/3 rearrangement with known partner\* (n = 60)
- Cohort B: Known or likely activating mutations (excluding kinase domain) in FGFR1-3 included in [Appendix C](#) (n = 90)
- Cohort C: FGFR1-3 known activating mutations in kinase domain; FGFR1-3 putatively activating mutations; other FGFR1/3 rearrangements\* (not eligible for Cohort A; n = 20)

\*Only FGFR fusions or rearrangements with an intact kinase domain are eligible.

Please note that there is no difference in the treatment regimen between the cohorts.

[figure not shown]
The sponsor may choose to cap enrollment of any one tumor type and/or FGFR alteration to allow representation of multiple tumor types and avoid analysis being influenced by any one tumor type. The sponsor may also choose to cap enrollment of any one tumor type if no benefit is being seen in previous participants enrolled.

For participants with FGFR2-rearranged cholangiocarcinoma, enrollment is limited to no more than 10 into Cohort A; for participants with FGFR3 mutation or fusions bladder cancer, enrollment is limited to no more than 10 participants into Cohort A or B combined. Participants from either group noted must have mandatory baseline and at least 1 on-treatment biopsy.

A fresh biopsy at baseline (or archival tissue that was collected less than 24 months from date of screening) and at least 1 on-treatment biopsy is required for participants with safely accessible lesions. Treatment will start on Day 1. Participants will undergo regular safety assessments during treatment as well as regular efficacy assessments. Participants will be allowed to continue administration in 21-day cycles until documented disease progression or unacceptable toxicity is reported.

**Figure 1: Study Design Schema**

\*Only FGFR fusions or rearrangements with an intact kinase domain are eligible.

CR = complete response; D/C = discontinue; FGF = fibroblast growth factor; FGFR = fibroblast growth factor receptor; PD = progressive disease; PR = partial response; SD = stable disease; SF = screen failure; tx = treatment.

Adherence to the study design requirements, including those specified in the SoA (see [Table 3](#) and [Table 4](#)), is essential and required for study conduct.

**Table 3: Schedule of Activities**

Visit Day (Range)	Screening	Treatment			EOT	Follow-Up		Survival	Notes
	Days -35 to -1	Cycle 1		Cycles 2+		Safety	Disease		
		Day 1	Day 8 ( $\pm 3$ d)	Day 15 ( $\pm 3$ d)		Day 1 ( $\pm 3$ d)	EOT + 30-35 d		
							Every 9 wk $\pm 7$ d		
Administrative procedures									
Informed consent	X								See Section 8.1.1.
Contact IRT	X	X	X	X	X	X			
Inclusion/exclusion criteria	X								
Prior treatments, procedures, surgery for disease	X								
General and disease medical history	X								
Prior/concomitant medications	X	X	X	X	X	X	X		
Dispense/administer pemigatinib		X	X	X	X*				*Assess for up-titration.
Collect study drug and review diary cards			X	X	X	X			
Safety assessments									
Slit lamp, visual acuity, funduscopic with digital imaging (eye)	X				X*	X			*Once every 3 cycles starting at Cycle 3 ( $\pm 7$ days), as well as clinically indicated.
Optical coherence tomography	X*				X*	X*			*Required at baseline and every 3 cycles, as well as when clinically indicated.
AE assessments	X	X	X	X	X	X	X		
Physical examination	X	X	X	X	X	X	X		
Vital signs/body weight/height	X	X			X	X	X		Height at screening only.
12-lead ECG	X	X			X	X	X		
ECOG	X	X			X	X	X		
Efficacy assessments									
CT or MRI	X				X*	X**		X	*Once every 3 cycles starting at the end of Cycle 3 ( $\pm 7$ days). **Perform at EOT if not done within 1 month prior to EOT.
Survival								X	

**Table 4: Schedule of Laboratory Assessments**

Visit Day (Range)	Screening	Treatment			EOT	Follow-Up		Survival	Notes
	Days -35 to -1	Cycle 1		Cycles 2+		Safety	Disease		
		Day 1	Day 8 (± 3 d)	Day 15 (± 3 d)		Day 1 (± 3 d)	(EOT + 30-35 d)		
							Every 9 wk ± 7 d		
Clinical laboratory assessments									
Blood chemistries	X	X*	X	X	X**	X	X		*If screening performed within 3 days of C1D1, additional sample not required. **HP in Cycle 1 requires Day 8 testing of serum phosphate in Cycle 2+.
Hematology	X	X*			X	X			*If screening performed within 3 days of C1D1, additional sample not required.
Coagulation	X	X			X	X			*If screening performed within 3 days of C1D1, additional sample not required.
Endocrine (PTH only)	X				X*	X			*Every 3 cycles on Day 1 starting with Cycle 3.
HBV/HCV testing	X								
Urinalysis	X					X			
Pregnancy testing	X*	X			X	X*			*Serum.
translational laboratory assessments									

**Table 4: Schedule of Laboratory Assessments (Continued)**

Visit Day (Range)	Screening	Treatment			EOT	Follow-Up		Survival	Notes				
	Days -35 to -1	Cycle 1		Cycles 2+		Safety	Disease						
		Day 1	Day 8 (± 3 d)	Day 15 (± 3 d)		Day 1 (± 3 d)	(EOT + 30-35 d)						
							Every 9 wk ± 7 d						
translational laboratory assessments (continued)													
Genomic testing													
Tumor tissue sampling	X*				X**	X***			*Mandatory tissue at baseline; archival tissue allowed if less than 12 months from date of screening.				
Buccal swab	X												

## 2. INTRODUCTION

### 2.1. Background

Pemigatinib is an inhibitor of the FGFR family of receptor tyrosine kinases that is proposed for the treatment of solid tumor malignancies with an activating FGFR mutation or translocation (fusion/rearrangement). Aberrant signaling through FGFR resulting from gene mutations or chromosomal fusions/rearrangements has been demonstrated in multiple types of human cancers. Fibroblast growth factor receptor signaling contributes to the development of malignancies by promoting tumor cell proliferation, survival, migration, and angiogenesis. Incyte is proposing to study pemigatinib for the treatment of solid tumor malignancies harboring an activating FGFR mutation or fusion/rearrangement.

#### 2.1.1. Fibroblast Growth Factor Receptor Inhibitor in Oncology

The mammalian FGFR family is composed of 4 highly conserved receptors (FGFR1, FGFR2, FGFR3, and FGFR4) that have an extracellular ligand-binding domain, a single transmembrane domain, and an intracellular tyrosine kinase domain. Eighteen FGR ligands, divided into canonical and hormonal FGFRs, bind to FGFRs, leading to receptor dimerization, activation of the kinase domain, and transphosphorylation of the receptors (Eswarakumar et al 2005).

Subsequent signal transduction occurs through phosphorylation of substrate proteins, such as FGFR substrate 2, which leads to activation of the RAS-mitogen-activated protein kinase and phosphoinositide 3-kinase-protein kinase B pathways and of the phospholipase C $\gamma$  that activates the protein kinase C pathway. In some cellular context, signal transducer and activator of transcription proteins are also activated by FGFRs. Signaling through the FGF-FGFR pathway is tightly controlled through feedback regulation. Mitogen-activated protein kinase phosphatases and Sprouty proteins are upregulated upon FGFR stimulation and antagonize FGF-dependent activation of extracellular signal-regulated kinases. In many cases, FGFR pathway activation promotes cell proliferation, survival, and migration; however, cellular context plays an important role, and in certain tissues, FGFR signaling results in growth arrest and cellular differentiation (Dailey et al 2005).

In adults, FGF-FGFR signaling is involved in angiogenesis during wound healing. The hormonal FGF ligands contribute to regulation of metabolic pathways involving lipid, glucose, phosphate, and vitamin D (Itoh 2010). Genetic defects in the FGF23-signaling pathway lead to disordered phosphate metabolism: loss of function mutations in FGF23 or its signaling results in retention of phosphate and tissue mineralizing, while gain of function mutations in the FGF23 pathway manifests as hypophosphatemic rickets syndrome (Farrow and White 2010).

Strong genetic and functional evidence supports that dysregulation of FGFR can lead to the establishment and progression of cancer. Genetic alterations in FGFR-3 have been described in many tumor types (Knights and Cook 2010, Turner and Grose 2010). These include activating mutations, translocations, and gene amplification resulting in ligand-independent constitutive activation of the receptors or aberrant ligand-dependent signaling through FGFRs.

A substantial body of evidence supports that a genetically activated FGFR pathway sensitizes FGFR-altered cancer cells to knockdown or inhibition of these receptors (Kunii et al 2008, Qing et al 2009, Weiss et al 2010, Lamont et al 2011). A large screen of more than 500 tumor

cell lines with a selective FGFR inhibitor demonstrated that only a small percentage (5.9%) of all cells are sensitive to FGFR inhibition, and growth-suppressed cell lines were highly enriched for FGFR alterations (Guagnano et al 2012). These results demonstrate that FGFR inhibitors are active in a targeted manner against cancers with activated FGFR pathway. An implication of these data is that selection based on molecular-, genetic-, or protein-based diagnostic tests for specific FGFR alterations in tumors may be important for identifying patients most likely to benefit from an FGFR inhibitor.

### 2.1.2. Solid Tumor Malignancies With Activating FGFR Mutations and Fusions/Rearrangements

Activation of the FGFR pathway by mutation or rearrangement is well-recognized as an oncogenic event in cancer. A recent survey of 4853 solid tumors identified FGFR1-3 mutations or rearrangements in 2.25% of all tumors tested (Helsten et al 2016). Analysis of FGFR1-3 mutations and rearrangements in the TCGA database (NCI 2018), demonstrate that FGFR alterations are not restricted to one tumor type, but rather broadly distributed across a diverse range of tumors (see Table 5). Importantly, preclinical and clinical data support the use of FGFR inhibitors in FGFR altered cell lines and tumors derived from a variety of cancer types, including bladder cancer, cholangiocarcinoma, endometrial cancer, and glioma and squamous lung cancer (Porta et al 2017).

**Table 5: Tumors With Frequency > 1% for FGFR1-3 Mutations and Rearrangements in TCGA**

Tumor Type	FGFR1		FGFR2		FGFR3		Total (%)
	Mutation (%)	Fusion (%)	Mutation (%)	Fusion (%)	Mutation (%)	Fusion (%)	
Urothelial carcinoma	0	0	0.75	0	12.64	3.15	16.54
Cholangiocarcinoma	0	0	0	13.9	0	0	13.9
Endometrial carcinoma	0	0	9.68	0.18	0	0	9.86
Glioblastoma multiforme	0.48	0	0	0	0.48	8.62	9.58
Lung squamous cell carcinoma	0.21	0.2	1.45	0.2	1.45	1.4	4.91
Cervical carcinoma	0	0	0.51	0	0	1.97	2.48
Renal papillary cell carcinoma	0	0	0	0	1.41	0.68	2.09
Rectal adenocarcinoma	0	0	2.01	0	0	0	2.01
Head and neck squamous cell carcinoma	0	0	0	0	1.14	0.76	1.9
Low grade glioma	0.19	0	0	0	0	1.71	1.9
Uterine carcinosarcoma	0	0	1.75	0	0	0	1.75
Esophageal adenocarcinoma	0	0.54	0	0	0	1.08	1.62
Stomach adenocarcinoma	0.25	0	0.5	0.48	0.25	0	1.48
Prostate adenocarcinoma	0	0	0	1.2	0	0.2	1.4
Breast (invasive) carcinoma	0	0.36	0.6	0.36	0	0	1.32
Adrenocortical carcinoma	0	0	1.1	0	0	0	1.1
Pheochromocytoma and paraganglioma	1.09	0	0	0	0	0	1.09
Colorectal adenocarcinoma	0.27	0	0.54	0	0.27	0	1.08
Skin cutaneous melanoma	0.21	0	0.84	0	0	0	1.05

Based on these observations, an FGFR inhibitor may be active across a variety of tumor types with activating mutations and gene fusions of FGFR1-3.

## **2.2. Study Rationale**

Pemigatinib is a potent selective inhibitor of FGFR1-3. This compound is proposed for the treatment of participants with advanced/metastatic or surgically unresectable solid tumor malignancies harboring activating FGFR mutations or fusions/rearrangements.

### **2.2.1. Scientific Rationale for Study Design**

The planned study will evaluate the efficacy and safety of pemigatinib as treatment in participants with advanced/metastatic or unresectable solid tumor malignancy with an activating FGFR mutation or fusion/rearrangement. Preliminary data from the ongoing Phase 1 study (INCB 54828-101) in second-line or greater treatment in all tumor types have shown interesting efficacy signals (ORR, PFS) and tolerable safety in participants with activating FGFR alterations.

The proposed study design is a single arm, open-label study of pemigatinib. An independent central radiology group will evaluate tumor response to support the primary and secondary endpoints to minimize bias.

### **2.2.2. Justification for Dose and Regimen**

Pemigatinib will be administered at 13.5 mg QD, continuously, for a cycle. Each cycle is 3 weeks. This dose and dosing schedule was selected based on emerging clinical and safety data from the INCB 54828-101 study, where the continuous dosing regimen was tested and has been tested in 12 and 14 participants at 9 mg and 13.5 mg QD continuous administration, respectively. In Study INCB 54828-101, the emerging safety data demonstrated that tolerability of the continuous dosing regimen of pemigatinib was comparable to that of intermittent dosing.

[figure not shown]
The hypothesis with a targeted therapy is that continued inhibition of the aberrant receptor may increase the potential for benefit from the treatment. Therefore, administering pemigatinib continuously will allow that consistent inhibition of the aberrant FGFR receptor in this population. Continuous dosing would still allow for dose holds for safety reasons with criteria and procedures for dose interruptions and adjustments clearly outlined in the Protocol.

Hyperphosphatemia is an expected on-target pharmacological effect of FGFR inhibition. The incidence of hyperphosphatemia, defined as any postbaseline phosphate level exceeding 5.5 mg/dL, has been observed in the majority of study participants treated with pemigatinib (refer to the [IB](#) for complete data). Some participants do not achieve hyperphosphatemia, and it is estimated that pharmacological concentration of pemigatinib in these participants is lower (see [Figure 2](#)). Therefore, up-titration of pemigatinib will be used to increase the exposure of pemigatinib in participants who do not achieve hyperphosphatemia when treated with 13.5 mg QD. The goal is to increase the serum concentration of pemigatinib.

The increase in serum phosphorus observed after treatment with pemigatinib was exposure-dependent and followed a sigmoid relationship. A population  $E_{max}$  model of pemigatinib AUC and maximal serum phosphate change from baseline was developed. For those participants treated with pemigatinib 13.5 mg who did not develop hyperphosphatemia,

AUC for pemigatinib 18 mg was estimated using a linear exposure relationship. Maximal serum phosphate change from baseline for each individual was then estimated using a population model. The maximal serum phosphate after treatment with pemigatinib 18 mg was calculated by adding the baseline of serum phosphate. The simulation suggested that the serum phosphate would increase above 5.5 mg/dL after treatment with pemigatinib 18 mg for the participants treated with pemigatinib 13.5 mg who did not develop hyperphosphatemia.

**Figure 2: Comparison of Steady-State Exposures for Pemigatinib 13.5 mg QD Between Participants With Nonhyperphosphatemia and Hyperphosphatemia (C1D8)**

AUCss = area under the curve at steady state; HP = hyperphosphatemia.

Any participant who does not reach the target serum phosphate level of > 5.5 mg/dL at any time during Cycle 1, and who is compliant with taking study drug and does not experience an ongoing Grade 2 or higher treatment-related AEs, will increase the daily dose to 18 mg starting at Cycle 2 Day 1.

A CYP3A4-mediated drug-drug interaction study (INCB 54828-104) indicated there is evidence of a clinically significant effect on pemigatinib exposure when coadministered with a potent CYP3A4 inhibitor, itraconazole (increased pemigatinib AUC by 88%) or potent CYP3A4 inducer, rifampin (decreased pemigatinib AUC by 85%). A PBPK model was developed and validated using in vitro and clinical DDI data. PBPK model–simulated pemigatinib AUCs were increased by approximately 50% for moderate CYP3A4 inhibitors and decreased by more than

50% for moderate CYP3A4 inducers. In addition, PBPK modeling shows no DDI effect when pemigatinib was coadministered with a weak CYP3A4 inhibitor or inducer.

Dose modifications for tolerability issues are noted in Section [6.5](#).

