15. Active chronic or current infectious disease requiring systemic antibiotic, antifungal, or antiviral treatment within 2 weeks before enrollment (participants with asymptomatic chronic infections on prophylactic treatment are allowed).
16. Evidence of active HBV or HCV infection (defined as participants with elevated transaminases or cirrhosis. Participants with chronic HBV/HCV infection with no cirrhosis and no elevated transaminases are allowed).
17. Known HIV infection.
18. Current use of prohibited medication as described in Section [6.6.2](#).
19. Use of any potent CYP3A4 inhibitors or inducers or moderate CYP3A4 inducers within 14 days or five half-lives (whichever is longer) before the first dose of study drug/treatment. Note that moderate CYP3A4 inhibitors are not prohibited.
20. Known hypersensitivity or severe reaction to pemigatinib or excipients of pemigatinib (refer to the [IB](#)).
21. Inability or unlikelihood of the participant to comply with the dose schedule and study evaluations, in the opinion of the investigator.
22. Inadequate recovery from toxicity and/or complications from a major surgery before starting therapy.
23. Women who are pregnant or breastfeeding.
24. Any condition that would, in the investigator's judgment, interfere with full participation in the study, including administration of study drug/treatment and attending required study visits; pose a significant risk to the participant; or interfere with interpretation of study data.
25. Inability of the participant (or parent, guardian, or legally authorized representative) to comprehend the ICF or unwillingness to sign the ICF.
26. History of hypovitaminosis D requiring supraphysiologic doses (eg, 50,000 UI/weekly) to replenish the deficiency. Vitamin D supplements are allowed.

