### 6.5.3. Up-Titration

Any participant who does not reach the target serum phosphate level of  $> 5.5$  mg/dL at any time during Cycle 1, are compliant with taking study drug, and do not experience an ongoing Grade 2 or higher treatment-related AEs will increase the daily dose to 18 mg starting from Cycle 2 Day 1.

Participants who are titrated up to 18 mg QD will begin the next cycle at the new dose level and must agree to all Cycle 1 assessments (█ safety assessments [hematology and blood chemistry]). Up-titration may occur no earlier than on Day 1 of Cycle 2, so that participants are observed for phosphate level and AEs at least for 1 cycle.

For participants who are up-titrated from 13.5 mg to 18 mg, dose reductions are allowed (see Section 6.5.1).

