### **6.6.1. Restricted Medications and Procedures**

Pemigatinib is predominantly metabolized by CYP3A4. There is an expected 50% increase in exposure in participants who concomitantly use CYP3A4 moderate inhibitors. However, as doses above the recommended Phase 2 dose of 13.5 mg QD have been tested (20 mg QD is tolerable), there is a sufficient safety margin. Therefore, the use of moderate CYP3A4 inhibitors is not prohibited but should involve careful monitoring, especially in relation to safety, while moderate CYP3A4 inducers and potent CYP3A4 inhibitors and inducers are prohibited (see [Appendix D](#)).

Careful monitoring is required when pemigatinib is concomitantly administered with OCT2 substrates such as dofetilide and metformin.

Calcium-based phosphate–binding medications should not be used due to a concern for soft tissue mineralization.

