### **6.6.2. Prohibited Medications and Procedures**

The following medications and measures are prohibited:

- The concomitant administration of potent CYP3A4 inhibitors and inducers and moderate CYP3A4 inducers (see [Appendix D](#)). Based on the low overall bioavailability of topical ketoconazole, there are no restrictions on topical ketoconazole.
- Any concomitant use of a selective FGFR inhibitor (other than pemigatinib).
- Investigational study drug for any indication.
- Use of any anticancer medications other than the study medications being tested in this Protocol.

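### The safety margin in Protocol 6.6.1 for moderate CYP3A4 inhibitors is argued from 13.5 mg, but the up-titration rule sends participants to 18 mg with no condition on these inhibitors

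*Protocol*

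**What the plan says.** **Up-titration.** Protocol 2.2.2 gives the trigger: a participant who "does not reach the target serum phosphate level of > 5.5 mg/dL at any time during Cycle 1". Section 6.5.3 repeats it and says that such a participant "will increase the daily dose to 18 mg starting from Cycle 2 Day 1". Two further conditions apply: compliance with study drug, and no ongoing treatment-related AE of Grade 2 or higher. Concomitant medication is not among the conditions.

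**Moderate inhibitors.** Exclusion criterion 19 in Protocol 5.2 says: "Note that moderate CYP3A4 inhibitors are not prohibited". The prohibition in 6.6.2 covers "The concomitant administration of potent CYP3A4 inhibitors and inducers and moderate CYP3A4 inducers" and so leaves moderate inhibitors out.

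**The justification.** Section 6.6.1 states: "There is an expected 50% increase in exposure in participants who concomitantly use CYP3A4 moderate inhibitors". It then refers to experience with doses higher than 13.5 mg QD and concludes: "20 mg QD is tolerable), there is a sufficient safety margin". It asks for careful monitoring. The only study dose it names is 13.5 mg; 18 mg does not appear.

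**Dose and exposure.** Section 2.2.2 says: "AUC for pemigatinib 18 mg was estimated using a linear exposure relationship". The same section gives a model-based AUC increase of about 50% for moderate inhibitors.

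**The concern.** Two provisions were each justified separately, and the protocol allows them together. Permission for moderate inhibitors rests on a margin worked out at the starting dose. The up-titration rule then raises the dose by a third (18 / 13.5 = 1.33), in mandatory wording, without asking whether that margin still holds.

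The combination is plausible. Appendix D lists ciprofloxacin, erythromycin and fluconazole as moderate inhibitors. In Table 7, urinary tract infection was reported in 37 of 261 continuous-dosing participants (14.2%). In the same table, 182 of 261 (69.7%) had a hyperphosphatemia AE, so 79 of 261 (30.3%) did not. That is an AE count over all of treatment and not a Cycle 1 phosphate result, so it shows only that up-titration is unlikely to be rare.

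What is at stake is participant safety at 18 mg and whether the stated safety argument is complete. The primary ORR analysis does not depend on it.

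**Working it through.** **Inputs**

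- Starting dose 13.5 mg QD (Protocol 6.1); up-titrated dose 18 mg QD (2.2.2, 6.5.3).
- Exposure increase with a moderate inhibitor: 50% (6.6.1; about 50% from the model in 2.2.2).
- Tolerable reference dose: 20 mg QD (6.6.1).
- Exposure proportional to dose, as 2.2.2 assumes in going from 13.5 mg to 18 mg.

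**Formula.** Dose-equivalent = dose x (1 + fractional AUC increase). This is the dose that, without an inhibitor, would give the same expected exposure.

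**Step 1: reproduce the argument in 6.6.1 at 13.5 mg.** 13.5 x 1.50 = 20.25 mg-equivalent, and 20.25 / 20 = 1.0125. Expected exposure is about 1% above the reference, so the argument holds approximately.

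**Step 2: the same calculation at 18 mg.** 18 x 1.50 = 27 mg-equivalent.

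- 27 / 20 = 1.35, or 35% (7 mg) above the reference.
- 27 / 13.5 = 2.00, or twice the expected exposure of 13.5 mg alone.

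Without an inhibitor, 18 mg is 18 / 20 = 0.90 of the reference. The issue is therefore the combination and not 18 mg alone.

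**Step 3: the inhibition each dose can absorb before reaching 20 mg-equivalent.**

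- At 13.5 mg: 20 / 13.5 - 1 = 48.1%.
- At 18 mg: 20 / 18 - 1 = 11.1%.

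**Step 4: sensitivity to the 50% figure.** The range of 25% to 75% is an assumption.

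| AUC increase | 13.5 mg | 18 mg |
|---|---|---|
| 25% | 16.9 mg-eq | 22.5 mg-eq |
| 50% | 20.25 mg-eq | 27.0 mg-eq |
| 75% | 23.6 mg-eq | 31.5 mg-eq |

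At 18 mg every value in this range exceeds 20 mg-equivalent.

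**Step 5: allowance for lower individual exposure.** Section 2.2.2 estimates that participants without hyperphosphatemia have lower concentrations. For 18 mg with an inhibitor to come down to 20 mg-equivalent, a participant's own exposure at a given dose would have to be 20 / 27 = 0.74 of the reference, or 26% lower. The size of the difference is shown in Figure 2, which is not available in the text reviewed, so this cannot be checked here.

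**The case against.** **20 mg is not a ceiling.** This stands. Section 6.6.1 calls 20 mg tolerable and does not call it maximal; even the 13.5 mg case slightly exceeds it. Section 2.3 reports no dose-limiting toxicities on monotherapy, and the Investigator's Brochure may hold supporting data that are not in these documents. So the finding is that the written justification does not reach 18 mg. It is not that 27 mg-equivalent has been shown to be unsafe.

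**Up-titrated participants may start from lower exposure.** This stands in part. It may offset some of the excess (step 5), most plausibly in someone who took the inhibitor throughout Cycle 1 and still stayed at or below 5.5 mg/dL. It is weaker when the inhibitor is started after the Cycle 1 samples or after up-titration.

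**Existing safeguards cover it.** Section 6.5 asks for judgment and medical monitor consultation on dose modifications, but frames this around AEs and their relatedness. The monitoring in 6.6.1 carries no dose condition. After up-titration the Cycle 1 safety assessments are repeated, Table 13 applies and dose reduction is available. These act after the exposure has risen, so they limit the harm but do not fill the gap at the dose decision.

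**The comparison with itraconazole.** A reader might infer that the permitted combination is worse than a prohibited one, since 27 mg-equivalent exceeds 13.5 x 1.88 = 25.38. That comparison mixes doses: at 18 mg itraconazole would give 18 x 1.88 = 33.84. It should carry no weight.

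**Conclusion.** The point holds as a gap in the dosing rules. The margin in 6.6.1 supports a moderate inhibitor at 13.5 mg. Nothing in the protocol extends it to 18 mg, where expected exposure is about 27 mg-equivalent, 35% above the cited dose. This rests on linear exposure up to that level and on the same 50% increase at 18 mg. The number of participants affected cannot be calculated, because the documents do not give the use of moderate inhibitors or the Cycle 1 phosphate response. No endpoint, power or alpha depends on it.

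A reader might go further and infer that a participant first above 5.5 mg/dL at the Day 22 predose draw must still go to 18 mg, and that this causes the 27 mg-equivalent. The documents do not support either step. That reading rests on SAP 4.1.5, a data-handling convention that starts Cycle 2 on its first dosing day. Against it, Table 3 places the up-titration assessment at the Cycles 2+ visit, Protocol 8.3.6 requires review of predose results before a new cycle, and 2.2.2 defines hyperphosphatemia by any postbaseline value and reserves up-titration for those without it. Nor does the 27 mg-equivalent depend on that sample: it applies to any up-titrated participant on a moderate inhibitor, whatever the Day 22 phosphate.

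**What to change.** Two edits:

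1. In 6.5.3 add: *A participant taking a moderate CYP3A4 inhibitor is up-titrated only with medical monitor agreement, because the margin in Section 6.6.1 applies to 13.5 mg.*
2. In 6.6.1 state that the margin was derived for 13.5 mg, and that starting a moderate inhibitor in a participant on 18 mg requires prior discussion with the medical monitor. The first edit alone would miss inhibitors started after up-titration.

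If the sponsor holds data supporting about 27 mg-equivalent, citing them in 6.6.1 would supply the missing justification.

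**Cost.** No new visit, sample or data item: Table 3 already records concomitant medications at the visit where up-titration is assessed. There will be some extra medical monitor contacts, and a few participants may have the increase delayed or withheld.

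Separately, and as a minor wording matter, 6.5.3 could say whether the predose Cycle 2 Day 1 phosphate counts toward the rule. That would not close the gap described here.
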